2. INTRODUCTION

PF-06462700 (Brand name in the US: ATGAM) is classified as an immunosuppressant/immunosuppressive agent. It is the purified, concentrated, and sterile gamma globulin, primarily monomeric immunoglobulin G (IgG), from hyperimmune serum of horses that are immunized with human thymus lymphocytes. PF-06462700 has a strong T-lymphocyte suppressive effect based on non-clinical studies results.

PF-06462700 has been authorized in global markets for more than 30 years where it is registered for 2 indications: 1) treatment of moderate to severe aplastic anemia, and 2) supportive treatment of renal allograft transplantation. In the US, the indication of treatment of moderate to severe aplastic anemia was approved in May 1985. In Europe Union (EU), a marketing authorisation application (MAA) was submitted by the decentralized procedure in 2014 and review is on-going. There are current national authorizations for both indications in the EU Member States Latvia and Slovenia

In Japan, the development was started in 1992 by limiting the targets to aplastic anemia, and the product was designated as an orphan drug in November 1993. Since the number of patients is small, it was difficult to conduct usual phase 2 and phase 3 clinical studies, and therefore, a general clinical study was conducted with 2 dose groups, and then the efficacy and safety in Japanese patients with aplastic anemia were confirmed. After that, for the indication of moderate/severe aplastic anemia with dosage and administration of 10-20 mg/kg per day for 8 days, a drug importing approval application was made by Pharmacia & Upjohn Company Inc. (current: Pfizer Japan Inc.) in CCI

PF-06462700 was evaluated as having high medical needs at the 36th meeting of the Study Group on Unapproved and Off-label Drugs of High Medical Need (held on 17 October 2018), and its development was requested by the Research and Development Division, Health Policy Bureau, Ministry of Health, Labor and Welfare on 12 November 2018 for the request contents described below.

Indication	Moderate and above aplastic anemia
Posology	The usual dosage for slow intravenous infusion is 40 mg of anti-human thymocyte immunoglobulin, equine, per 1 kg of body weight once daily, for 4 days.

2.1. Study Rationale

The purpose of the study is to assess the efficacy and safety of PF-06462700 administered intravenously at 40 mg/kg/day for 4 days in Japanese participants with moderate and above aplastic anemia for making a new drug application in Japan.

The outline of the study was agreed upon with the Pharmaceutical and Medical Device Agency (PMDA) on 27 September 2019.

2.2. Background

2.2.1. Mechanism of Action/Indication

The mechanism of PF-06462700-induced immunosuppression has not been definitively determined. However, published data indicate that rapid, reversible depletion of circulating lymphocytes is a consistent finding of PF-06462700 treatment, with greatest effect on T-lymphocytes.^{1,2} Lymphocyte depletion may be caused by complement dependent lysis^{3,4,5} and/or activation induced apoptosis.^{6,7} In addition, immunosuppression may be mediated by the binding of antibodies to lymphocytes, which results in partial activation and induction of T-lymphocyte anergy.⁸

While the mechanism of PF-06462700 in treating aplastic anemia is attributed in large part to its immunosuppressive activity against effector cytotoxic T cells, PF-06462700 has also been shown to directly stimulate growth of hematopoietic stem cells in vitro,^{3,6,9} and release hematopoietic growth factors such as interleukin-3 and granulocyte/macrophage colony stimulating factor.¹⁰ Greater sensitivity of peripheral blood mononuclear cells (PBMC) from aplastic anemia patients to these stimulatory actions of PF-06462700 also may account for its efficacy. H³-thymidine incorporation in vitro in PBMC from both normal volunteers and aplastic anemia patients was increased following incubation with 2.5 or 5 µg/mL of PF-06462700 for 72 hours, indicative of cell proliferation.⁸ Cells from patients were more responsive than cells from normal volunteers.¹¹

2.2.2. Background of Aplastic Anemia

Aplastic anemia (AA) is a syndrome characterized by a decrease in all blood cells in peripheral blood (pancytopenia) and a decrease in bone marrow cell density (hypoplasia). In fact, there are many diseases that show these laboratory findings, and therefore it is possible to diagnose AA only by excluding other diseases with more definite concepts. It can be said that the essential nature of the disease is a “state of having a characteristic decrease in hematopoietic stem cells despite the absence of effects of myelotoxic drugs.”¹²

2.2.2.1. Diagnostic criteria

Table 1 shows the revised diagnostic criteria proposed by the Study Group on Idiopathic Hematopoietic Disorders, Research Program on Rare and Intractable Diseases, Health, Labor and Welfare Sciences Research Grants, which is the diagnostic criteria in Japan.

Internationally, AA is diagnosed only when 2 or more of the 3 criteria [hemoglobin < 10 g/dL, neutrophils < 1,500/µL, and platelets < 100,000/µL] are met and the bone marrow is hypoplastic.¹³

Table 1. Diagnostic criteria for aplastic anemia (Revised in 2016) ¹²

1. Clinical findings include anemia, bleeding tendency, and sometimes pyrexia.
2. At least 2 of the following 3 criteria are met:
 - [1] Hemoglobin level < 10 g/dL, [2] Neutrophils < 1,500/ μ L, [3] Platelets < 100,000/ μ L
3. No other diseases that can cause pancytopenia. Other diseases commonly causing pancytopenia include leukemia, myelodysplastic syndrome, myelofibrosis, paroxysmal nocturnal hemoglobinuria (PNH), megaloblastic anemia, cancer bone marrow metastasis, malignant lymphoma, multiple myeloma, hypersplenism (cirrhosis, portal hypertension, etc.), systemic lupus erythematosus, hemophagocytic syndrome, and infection.
4. The following test findings increase the certainty of diagnosis:
 - 1) No increase in reticulocytes or immature platelets.
 - 2) Bone marrow aspiration findings (including clot specimens) show decreased nucleated cells in severe cases.

In non-severe cases, there may be no decrease in nucleated cells depending on the puncture site, but megakaryocytes have decreased.

When cells remain, erythroblasts often show dysplasia, but granulocytic dysplasia is not prominent.
 - 3) Bone marrow biopsy findings show decreased hematopoietic cell percentage.
 - 4) Increased serum iron levels and decreased unsaturated iron binding capacity.
 - 5) MRI of the thoracolumbar spine shows decreased hematopoietic cells and increased adipose tissue.
 - 6) Blood cells in paroxysmal nocturnal hemoglobinuria plasma are detected.
5. When making a diagnosis, aplastic anemia is suspected according to 1. and 2., other diseases are excluded according to 3., and the diagnosis is more definite according to 4. Diagnosis of aplastic anemia is basically based on exclusion of other diseases. However, in non-severe cases, it is difficult to differentiate from myelodysplastic syndrome with no increase in blast cells/ringed sideroblasts or chromosomal abnormality because morphological abnormality is often observed in bone marrow cells. Therefore, the treatment policy should be determined according to the pathological condition. Laboratory findings that may be useful in determining whether the patient has bone marrow failure due to immune pathology (immunosuppressive therapy is easy to become effective) include increases in PNH-type cells and cells with loss of HLA Class I alleles, and high plasma thrombopoietin levels (320 ng/mL).

2.2.2.2. Severity criteria

Since the prognosis and treatment policy of AA vary greatly depending on the severity, the severity should be determined according to the degree of cytopenia. In Japan, the severity is divided into 5 grades: very severe, severe, slightly severe, moderate, and mild ([Table 2](#)). Cases with a neutrophil count of less than 200/ μ L are called the very severe form because they have a high risk of severe infection or bleeding. The very severe form includes cases with an increase in neutrophils to some extent in response to granulocyte colony-stimulating factor (G-CSF) and the “fulminant type” in which there is no response to G-CSF and virtually no neutrophils.¹⁴

Table 2. Severity criteria for aplastic anemia (Modified in 2017)¹²

Stage 1	Mild	No blood transfusion is required other than the following:
Stage 2	Moderate	
	a	Two or more of the following criteria are met, and no red blood cell transfusion is required.
	b	Red blood cell transfusion is required, but the frequency is less than 2 units per month.
		Reticulocytes < 60,000/ μ L Neutrophils < 1,000/ μ L Platelets < 50,000/ μ L
Stage 3	Slightly severe	Two or more of the following criteria are met, and transfusion of 2 units or more of red blood cells is required every month.
		Reticulocytes < 60,000/ μ L Neutrophils < 1,000/ μ L Platelets < 50,000/ μ L
Stage 4	Severe	Two or more of the following criteria are met:
		Reticulocytes < 40,000/ μ L Neutrophils < 500/ μ L Platelets < 20,000/ μ L
Stage 5	Very severe	In addition to neutrophils < 200/ μ L, at least 2 of the following criteria are met:
		Reticulocytes < 20,000/ μ L Platelets < 20,000/ μ L

2.2.2.3. Epidemiology

The number of medical service recipients in Japan (prevalence) is approximately 11,000 in 2014 with a prevalence rate of 8.7 (/100,000 population). The number of incidence cases from 2004 to 2012 was approximately 9,500 (about 1,000 people per year), the incidence rate was estimated to be 8.2 (/1 million person-years)¹⁵. The sex ratio (female/male) of the incidence rate was 1.16, with a peak in both men and women in their 10s to 20s and 70s to 80s, and with a greater peak in the elderly. The incidence rates in western countries are reported to be 1.5 to 2.5 (/1 million person-years).^{16,17} The incidence rate in Japan is higher than these rates.¹²

2.2.2.4. Treatments

Treatments of aplastic anemia in Japan include supportive therapy and treatment aimed at hematopoietic recovery.¹²

2.2.2.4.1. Supportive therapies

Supportive therapies include blood transfusion (red blood cell transfusion, platelet transfusion, granulocyte transfusion) when anemia or thrombocytopenia is severe or associated with moderate or severe clinical symptoms, G-CSF administered when the neutrophil count is less than 500/ μ L and infection is concurrently present, and iron chelation therapy.¹²

2.2.2.4.2. Treatments aimed at hematopoietic recovery

Treatments aimed at hematopoietic recovery include (1) immunosuppressive therapy [Cyclosporine, anti-thymocyte globulin (ATG)], (2) anabolic steroid therapy (Methenolone

acetate, Danazol), and (3) hematopoietic stem cell transplantation. Treatment guidelines by severity have been shown.¹²

2.2.3. Clinical Overview

Brief descriptions of completed clinical studies are provided below. In this section, ATGAM and/or horse-ATG mean PF-06462700.

2.2.3.1. Overseas clinical studies

2.2.3.1.1. Study 3-197^{18,※1}

OBJECTIVE: To evaluate the efficacy of ATGAM for the treatment of aplastic anemia.

STUDY DESIGN: A randomized controlled study in which subjects are randomized to receive ATGAM or control treatment (supportive therapy alone). Subjects assigned to the control group were allowed to receive ATGAM at 3 months after initiation of study treatment.

TARGET PATIENTS: Patients with moderate to severe aplastic anemia who were not candidates for bone marrow transplantation.

DOSING REGIMEN FOR ATGAM: 20 mg/kg/day for 8 days.

SAMPLE SIZE: ATGAM group: N=21; Control group: N=20.

PRIMARY ENDPOINT: Response at 3 months after initiation of study treatment.

KEY RESULTS: The hematologic response rate at 3 months was statistically significantly higher in ATGAM group than in control group (47% vs 6%; p<0.01). In the patients treated with ATGAM including 11 patients in the control group who were treated with ATGAM after 3 months, the survival rate at 24 months was 62%. Fever, chills, and erythematous or urticarial rash were seen in all ATGAM treated patients. Platelet counts decreased during ATGAM infusion and daily platelet transfusions were necessary. Serum sickness occurred in all patients within 6 to 18 days of ATGAM initiation and was well-controlled with standard therapy. Three patients experienced transient hypotension.

2.2.3.1.2. Study 3-198

OBJECTIVE: To compare the response of ATGAM plus androgen in combination with HLA-mismatched transplantation or without HLA-mismatched transplantation.

STUDY DESIGN: An open-label, non-randomized controlled study in which subjects are assigned to receive either ATGAM plus androgen in combination with mismatched

※1 The results of Study 3-197 shown in the technical report by the sponsor and those in the published report (Champlin, 1983) are inconsistent because they have evaluated treatment response according to different definitions.

transplantation of bone marrow or only ATGAM plus androgen, according to the availability of an appropriate donor.

TARGET PATIENTS: Patients with severe aplastic anemia who were not candidates for bone marrow transplantation.

DOSING REGIMEN FOR ATGAM: 16 mg/kg/day for 10 days.

SAMPLE SIZE: with mismatched transplant: N=24; without mismatched transplant: N=18.

PRIMARY ENDPOINT: Response at 3 months a with mismatched transplant after initiation of study treatment.

KEY RESULTS: The hematologic response rates at 3 months in patients receiving mismatched transplant in addition to ATGAM plus androgen and in those treated with only ATGAM plus androgen were similar (43% and 44%, respectively). The survival rates at 12 months in those with mismatched bone marrow transplant and in those without it were 83% and 59%, respectively. The most commonly reported adverse events were rash, fever, arthralgias, chills, headache, myalgia and pruritus.

2.2.3.1.3. Study 5000¹⁹

OBJECTIVE: To compare the response of ATGAM with or without androgen.

STUDY DESIGN: A randomized, double-blind, controlled study in which subjects are randomized to receive either ATGAM plus androgen or ATGAM plus placebo.

TARGET PATIENTS: Patients with moderate to severe aplastic anemia who were not candidates for bone marrow transplantation.

DOSING REGIMEN FOR ATGAM: 20 mg/kg/day for 8 days.

SAMPLE SIZE: ATGAM plus androgen: N=26; ATGAM plus placebo: N=27.

PRIMARY ENDPOINT: Response at 6 months after initiation of study treatment.

KEY RESULTS: The hematologic response rates at 6 months in the ATGAM plus androgen group and ATGAM plus placebo group were similar (42% and 44%, respectively). The survival rates at 24 months in the ATGAM plus androgen group and ATGAM plus placebo group were 55% and 50%, respectively (when analyzed in only patients with severe disease). Adverse reactions in both groups were comparable and included rash, chills, gastrointestinal disturbances, and joint pain during ATGAM infusion, as well as symptoms of serum sickness in

all patients. Five patients had asymptomatic sinus bradycardia; six patients required antihypertensive therapy. Alanine transaminase or alkaline phosphatase levels increased to >2 times the upper limits of normal in 7 patients receiving ATGAM plus androgen, and in 9 patients receiving ATGAM plus placebo.

2.2.3.1.4. National Institutes of Health (NIH)-initiated clinical study¹

OBJECTIVE: To compare the efficacy and safety of ATGAM and rabbit-ATG in aplastic anemia.

STUDY DESIGN: A randomized controlled study in which subjects are randomized to receive ATGAM or rabbit-ATG.

TARGET PATIENTS: Patients with severe aplastic anemia.

DOSING REGIMEN FOR ATGAM: 40 mg/kg/day for 4 days, DOSING REGIMEN FOR rabbit-ATG: 3.5 mg/kg/day for 5 days.

SAMPLE SIZE: N=60/group.

KEY ENDPOINT: Hematologic response at 6 months after initiation of treatment.^{*1}

KEY RESULTS: The response rate at 6 months in the ATGAM group (68%) was significantly higher than that in the rabbit-ATG group (37%). The 3-year survival in the ATGAM group (96%) was significantly higher than that in the rabbit-ATG group (76%). As expected from the patient characteristics of the population in this study, the most frequently reported AEs were infections in both treatment groups. Mortality or disease exacerbation leading to study discontinuation was reported in 2 subjects treated with ATGAM and 9 subjects with rabbit-ATG. Serious adverse events (SAEs) for which at least 2 subjects were reported in the ATGAM group included neutropenic fever (negative cultures) (23 events), neutropenic fever (positive cultures) (17), upper respiratory infection (5), serum sickness, menorrhagia, Clostridium difficile infection, and tonsillitis/pharyngitis (2 each).

2.2.3.2. Japanese clinical study

2.2.3.2.1. An Upjohn (currently, Pfizer)-initiated clinical study²⁰

OBJECTIVE: To evaluate the efficacy and safety of ATGAM in the treatment of aplastic anemia.

STUDY DESIGN: An open-label, two-arm, randomized controlled study in which subjects are randomized to receive either ATGAM 10 mg/kg/day or 20 mg/kg/day.

TARGET PATIENTS: Patients with moderate to severe aplastic anemia who were not candidates for bone marrow transplantation.

DOSING REGIMEN FOR ATGAM: 10 or 20 mg/kg/day for 8 days.

SAMPLE SIZE: ATGAM 10 mg/kg/day: N=25; 20 mg/kg/day: N=25.

^{*1} Response was declared if the subject no longer met the criteria of severe aplastic anemia (hypoplasia of bone marrow (<30%) and fulfilment of at least 2 of the three conditions, neutrophil count <0.5×10⁹/L, reticulocyte count <60×10⁹/L, and platelet count <20×10⁹/L).

KEY ENDPOINT: Hematologic response at 6 months after initiation of treatment.*²

KEY RESULTS: Among 56 patients enrolled, 35 were included in the Efficacy Analysis Set, and 50 in the Safety Analysis Set. Overall, the percentage of patients who achieved moderate to marked hematologic improvement at 6 months after initiation of treatment was 28.6%, and that for mild to marked improvement was 42.9% (Moderate to marked improvement rate in the 10 mg/kg/day group: 21.1%; that in the 20 mg/kg/day group: 37.5%). Adverse reactions commonly reported for ATG and anti-lymphocyte globulin (ALG) products, including pyrexia, rash, headache/chills, and arthralgia were frequently reported in this study with one patient experiencing anaphylaxis; all of these events were manageable with an intervention.

2.2.3.2.2. A Prospective Study for Aplastic Anemia by the Investigative Research Team for Idiopathic Disorders of Erythropoiesis (a specific disease), the Ministry of Health and Welfare²¹

OBJECTIVE: To evaluate the efficacy of immunosuppressive therapy in aplastic anemia.

STUDY DESIGN: An open-label study.

TARGET PATIENTS: Patients with aplastic anemia (only those with severe disease were treated with ATGAM). Patients were initially treated with high doses of methylprednisolone, and then steroid-resistant patients were treated with ATGAM or with ALG.

DOSING REGIMEN FOR ATGAM: 40 mg/kg/day for 4 days.

SAMPLE SIZE: A total of 184 patients, including 13 treated with ATGAM.

KEY ENDPOINT: Hematologic response at 1 month after initiation of treatment.*³

KEY RESULTS: Among 13 ATGAM-treated patients, 1 patient achieved a good response, 3 did a minimal response, and 9 did no response at one month. Although only 1 patient

*² 1. Marked Improvement (case in which the severity as assessed per the “Severity Criteria for Aplastic Anemia of the Investigative Research Team for Idiopathic Disorders of Erythropoiesis (a specific disease), the Ministry of Health and Welfare” has changed from severe to mild or from severe to moderate or from moderate to mild, and hemoglobin level has increased ≥ 2 g/dL without transfusion), 2. Moderate Improvement (case in which the severity has unchanged from severe or from moderate, and hemoglobin level has increased ≥ 2 g/dL without transfusion), 3. Mild Improvement (case in which the severity has changed from severe to moderate or from moderate to mild, and hemoglobin level has not increased ≥ 2 g/dL without transfusion), 4. No Response (other cases)

*³ 1. Good Response (case in which the severity as assessed per the “Severity Criteria for Aplastic Anemia of the Investigative Research Team for Idiopathic Disorders of Erythropoiesis (a specific disease), the Ministry of Health and Welfare” has changed from severe to mild or from severe to moderate or from moderate to mild, and hemoglobin level has increased ≥ 2 g/dL without transfusion), 2. Partial Response (case in which the severity has unchanged from severe or from moderate, and hemoglobin level has increased ≥ 2 g/dL without transfusion), 3. Minimal Response (case in which the severity has changed from severe to moderate or from moderate to mild, and hemoglobin level has not increased ≥ 2 g/dL without transfusion), 4. No Response (other cases)

responded to ATGAM at 1 month, 1 of 3 patients with minimal response and 6 of 9 patients with no response achieved good response at 8 to 32 weeks. Thus, ATGAM was effective in Japanese patients with aplastic anemia as well.

2.3. Benefit/Risk Assessment

In this section, eATG means PF-06462700.

eATG has strong suppressive effects on T-lymphocyte based on results from non-clinical studies. The mechanism of eATG-induced immunosuppression has not been definitively determined. Published data indicate that rapid, reversible depletion of circulating lymphocytes is a consistent finding following administration of eATG, with greatest effect on T-lymphocytes. Lymphocyte depletion may be caused by complement dependent lysis and/or activation-induced apoptosis. In addition, immunosuppression may be mediated by the binding of antibodies to lymphocytes, which results in partial activation and induction of T-lymphocyte anergy.

Immune-mediated reactions

In rare instances, serious immune-mediated reactions have been reported with the use of eATG. Clinical signs associated with anaphylaxis, other infusion associated reactions, and serum sickness have been reported. Based on the mechanism of action of eATG, there is a potential risk of cytokine release syndrome.

A systemic reaction such as a generalized rash, tachycardia, dyspnea, hypotension, or anaphylaxis precludes any additional administration of eATG.

Infection

Monitor patients carefully for concurrent infection. Some studies have suggested an increase in the incidence of cytomegalovirus infection in patients receiving eATG²². Some physicians have found that it may be possible to reduce this risk by decreasing the dosage of other immunosuppressive agents which might be administered concomitantly with eATG.

In common with products derived from, or purified with human blood components, the possibility of transmission of some infectious diseases should be borne in mind.

Renal or hepatic impairment

In patients with aplastic anemia and other hematologic abnormalities who have received eATG, abnormal tests of liver function and renal function have been observed.

More detailed information about the known and expected benefits and risks and reasonably expected adverse events (AEs) of PF-06462700 may be found in the investigator's brochure, which is the single reference safety document (SRSD) for this study.

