7. DISCONTINUATION OF STUDY INTERVENTION AND PARTICIPANT DISCONTINUATION/WITHDRAWAL

7.1. Discontinuation of Study Intervention

In rare instances, it may be necessary for a participant to permanently discontinue investigational product. If investigational product is permanently discontinued, the participant will remain in the study to be evaluated for the assessments at the Early Termination (ET) and Follow-up visits (per [Schedule of Activities \(SoA\)](#)).

Note that discontinuation of investigational product does not represent withdrawal from the study.

See the [Schedule of Activities \(SoA\)](#) for data to be collected at the time of intervention discontinuation and follow-up and for any further evaluations that need to be completed.

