8. STUDY ASSESSMENTS AND PROCEDURES

The investigator (or an appropriate delegate at the investigator site) must obtain a signed and dated ICD before performing any study-specific procedures.

Study procedures and their timing are summarized in the [Schedule of Activities \(SoA\)](#). Protocol waivers or exemptions are not allowed.

Immediate safety concerns should be discussed with the sponsor immediately upon occurrence or awareness to determine if the participant should continue or discontinue study intervention.

Adherence to the study design requirements, including those specified in the SoA, is essential and required for study conduct.

All screening evaluations must be completed and reviewed to confirm that potential participants meet all eligibility criteria. The investigator will maintain a screening log to record details of all participants screened and to confirm eligibility or record reasons for screening failure, as applicable.

Procedures conducted as part of the participant's routine clinical management (e.g., blood count) and obtained before signing of the ICD may be utilized for screening or baseline purposes provided the procedures met the protocol-specified criteria and were performed within the time frame defined in the SoA.

Every effort should be made to ensure that protocol-required tests and procedures are completed as described. However, it is anticipated that from time to time there may be circumstances outside the control of the investigator that may make it unfeasible to perform the test. In these cases, the investigator must take all steps necessary to ensure the safety and well-being of the participant. When a protocol-required test cannot be performed, the investigator will document the reason for the missed test and any corrective and preventive

actions that he or she has taken to ensure that required processes are adhered to as soon as possible. The study team must be informed of these incidents in a timely manner.

The total blood sampling volume for individual participants in this study is approximately 60 mL. The actual collection times of blood sampling may change. Additional blood samples may be taken for safety assessments at times specified by Pfizer, provided the total volume taken during the study does not exceed 550 mL during any period of 60 consecutive days.

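### Protocol Section 7.1 can be read as sending participants who stop study drug down an early-termination path that ends before Week 12, so their primary endpoint could be lost

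*Protocol*

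**What the plan says.** **Visits after stopping study drug.** Protocol Section 7.1 says that after a permanent stop "the participant will remain in the study to be evaluated for the assessments at the Early Termination (ET) and Follow-up visits", as set out in the Schedule of Activities (SoA). It adds that stopping the product is not withdrawal from the study.

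Section 7.2 points two ways:
- It confines the early discontinuation visit to participants who were assigned to the product and then withdrawn early from the study. It treats them as leaving both treatment and study at that point.
- Under Withdrawal of Consent, it keeps participants who ask to stop treatment in the study and in the protocol's follow-up, unless they withdraw consent to further contact.

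The SoA (Section 1.3) puts ET in the same column as Week 24. Its last column is a follow-up of ET cases 28 days after ET, with a window of +7 days. Week 12 is Day 85 ±7 days.

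**What depends on it.** The primary endpoint is hematologic response at Week 12 (Protocol 8.1.1, SAP 3.1). Missing data are not imputed (Protocol 9.1.1 and 9.4.1, SAP 5.3 and 6.1.1.1). The full analysis set (FAS) holds everyone with at least one dose (Protocol 9.3, SAP 4). The target is 3 participants, and more are allowed (Protocol 9.2).

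**When dosing ends.** Section 2.3 states: "A systemic reaction such as a generalized rash, tachycardia, dyspnea, hypotension, or anaphylaxis precludes any additional administration of eATG". Section 8 states: "Immediate safety concerns should be discussed with the sponsor immediately upon occurrence or awareness to determine if the participant should continue or discontinue study intervention". Section 7.1 names no reaction criterion and refers to neither statement.

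**The concern.** Section 7.1 is where a site looks when dosing has been stopped. It says the participant stays in the study, but the visits it names are those the SoA uses for someone leaving early. Section 7.2 assigns the early visit to a different group. Two sites could handle the same early stop differently: one continues to Week 24, the other closes the participant out about a month after ET.

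For the second participant there would be no Week 12 assessment and no substitute value. With a minimum of 3 participants, each listed individually, one such case visibly weakens the only primary result the study produces. Those who stop early are also unlikely to be a random subset, so losing them could make the remaining listing look different from the treated group.

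The statements on when dosing ends have a similar weakness. An unqualified bar and a decision reached in discussion with the sponsor can lead to different actions after the same reaction. AEs leading to discontinuation are a safety endpoint, so different handling would also affect that listing.

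**Working it through.** No sample-size or power figure is there to be reproduced: the target of 3 rests on feasibility, and no testing is planned. The check is a comparison of texts plus day arithmetic.

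**1. Which visits apply after a stop without withdrawal?**

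| Place | Who it covers | What follows |
|---|---|---|
| 7.1 | Anyone who permanently stops the product | Remains in the study; ET and Follow-up visits |
| 7.2, main text | Those withdrawn early from the study | Early discontinuation visit; ends treatment and study |
| 7.2, Withdrawal of Consent | Those who ask to stop treatment | Remain in protocol follow-up |

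The SoA has no early discontinuation column other than ET, so I take the two names to mean the same visit. Section 7.1 then gives that visit to people who stay in the study, and 7.2 restricts it to people who leave. The term Follow-up visits does not settle the matter, because the SoA uses follow-up both for the Week 1 to Week 24 period and for the visit after ET.

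**2. Where does the ET path end?**

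Inputs: dosing on Days 1 to 4; ET assumed to be held on the day of stopping, since 7.1 gives no timing; follow-up 28 days after ET, +7.

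- Week 12 window: 85 − 7 = Day 78 to 85 + 7 = Day 92.
- Last visit for a stop on day d: Day d + 28 to Day d + 35.
- Gap from the latest permitted last visit to the opening of the window: 78 − (d + 35).

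| Stop and ET on | Last visit | Gap before Day 78 |
|---|---|---|
| Day 1 | Day 29 to 36 | 42 days |
| Day 2 | Day 30 to 37 | 41 days |
| Day 3 | Day 31 to 38 | 40 days |
| Day 4 | Day 32 to 39 | 39 days |

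Even with the full +7 days, the path falls short of Week 12 for every possible stopping day. For the last visit to reach Day 78, ET would have to be held on Day 43 or later (43 + 35 = 78).

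**3. What happens to the endpoint?**

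Counts would still be recorded at ET and its follow-up (Protocol 8.1.2), but response is defined only at Weeks 12 and 24. The SAP uses observed values at each designated visit and imputes nothing. A participant with one dose is in the FAS, so the Week 12 response would be blank. At the minimum sample size this is 1/3, or about 33%, of the primary data. The intercurrent-event text in Protocol 9.1.1 and SAP 2.1.1 does not mention stopping study drug.

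**4. Do the two statements on stopping agree?**

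Section 2.3 leaves no discretion for the reactions it names. Section 8 provides for a continue-or-stop decision on any immediate safety concern and makes no exception for those reactions. Neither refers to the other.

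**The case against.** The best defence is that most of the text favours continued follow-up. Section 7.1 says the participant remains and that stopping is not withdrawal. Section 7.2 limits the early visit to those who leave and requires follow-up of those who ask to stop. Follow-up visits in 7.1 may simply mean the SoA's Week 1 to Week 24 period. On that reading, Week 12 is observed and nothing is lost.

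This stands to the extent that the loss cannot be called certain. It does not remove the ambiguity. Section 7.1 still names ET, and the 7.2 follow-up sentence speaks of participants who request to stop, not of those stopped by the investigator after a reaction.

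On when dosing ends, one can argue that the Section 2.3 bar governs the reactions it lists and Section 8 covers everything else. That is a possible reconciliation, but the protocol does not state it.

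A reader might infer more than the documents support:
- **That 7.1 contradicts 2.3, or would let dosing continue.** Section 7.1 is silent on reactions. It permits permanent stopping without limiting the reasons.
- **That most courses would be stopped.** The summary of Study 3-197 says "Fever, chills, and erythematous or urticarial rash were seen in all ATGAM treated patients", but it does not call the rash generalized. The regimen was 20 mg/kg/day for 8 days, not 40 mg/kg/day for 4 days. The share that would meet Section 2.3 is not given.
- **That the wording "In rare instances, it may be necessary for a participant to permanently discontinue investigational product" is contradicted by earlier trials.** The trial summaries give no rate of stopping the product because of reactions. In the earlier Japanese study, the reactions are reported "with one patient experiencing anaphylaxis; all of these events were manageable with an intervention". Section 2.3 itself calls serious immune-mediated reactions rare.

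**Conclusion.** The point holds as an ambiguity about visits with a specific consequence. If a site follows the ET path after a stop on Days 1 to 4, the last visit falls between Day 29 and Day 39, and the unimputed Week 12 response is lost for that FAS participant. Each such case costs one third of the primary data at 3 participants, and less if more are enrolled.

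This rests on two assumptions: that ET is held on the day dosing stops, and that Section 7.1 is read as replacing the regular visits. The documents give no rate of early stopping, so I attach no probability to the loss. No alpha, power or sample-size figure is affected.

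Section 2.3 against Section 8 is a separate and smaller matter of reconciling two statements. It does not show that stopping will be frequent, and the point about Week 12 does not depend on it.

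**What to change.** 1. **Visits.** State in Section 7.1 that participants who permanently stop study drug stay on the regular schedule, including the Week 12 and Week 24 efficacy assessments, unless they withdraw consent for further follow-up or are withdrawn from the study. Reserve the ET visit and the visit 28 days later for withdrawal from the study, and use one name for that visit in 7.1, 7.2 and the SoA.
2. **Stopping statements.** The sponsor should reconcile Section 2.3 with Section 8 and cross-refer to the outcome in Section 7.1. Which clinical rule should apply is for the sponsor to decide; none is proposed here.

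The cost is amendment wording. The Week 12 and Week 24 visits are already in the SoA, and the SAP's listing of observed values needs no change. The added burden is that participants who stop early attend the same visits as those who complete dosing.
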